**Delivered Dose intensity ( $10^8$  pfu/week):**

If last dose before D43 visit (visit day  $\leq$  44)

- number of injections / [(Last dose date-1st dose date +7)/7]

If last dose on or after D43 visit (visit day  $>$  44):

- number of injections / [(Last dose date-1st dose date +7\*3)/7]

**Planned Dose intensity ( $10^8$  pfu/week):**

If last dose before D43 visit (visit day  $<$  42): 1

If last dose on or after D43 visit (visit day  $\geq$  42):

Given xx the theoretical study day of visit Dxx

$$\frac{6 + \text{Int}\left[\frac{(xx - 1 + 21 - 7 \times 6)}{21}\right]}{(\text{Last dose date} - \text{1st dose date} + 21)/7}$$

For example, at visit D85; then number of injections should be:  $6 + \text{int}((85-1+21-42)/21) = 9$

**Duration of exposure (weeks):** (Last dose date-1st dose date + 1)/7

All laboratory parameters will be expressed in the International System (SI) of units and the intensity grade using CTCAE version 5. A grade of 0 will be assigned when the value is within normal limits. In the case a local laboratory normal range overlaps into the higher (i.e., non-zero) CTC grade, the laboratory value will still be taken as within normal limits and assigned a CTC grade of 0. When normal limits are missing and needed for intensity grade determination, the grade will be set at missing. If normal limits are missing but not needed, grade intensity will be calculated as usual with CTCAE ranges.

Laboratory values recorded as “value  $<$  x” or “value  $>$  x” will be handled as the formula:

- $x = x * \sum_{i=1}^{n+2} (9 * 10^{-i})$  if value recorded as “value  $<$  x” with n denoted the number of significant digits
- $x = x * (1 + 10^{-n+2})$  if value recorded as “value  $>$  x” with n denoted the number of significant

digits

for the calculation of descriptive parameters and for the value derived in standard units. Other methods could be investigated for specific parameters. In individual listings, they will be presented as “< x” or “> x”.

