#### **8.3.1 Demographic and baseline characteristics**

Baseline demographics and disease characteristics data will be listed and summarized on SAF population.  
SAP-template version of 4 Jan 2024

The following continuous variables will be included:

- Date of ICF signature (listing only)
- Age at initial informed consent signature (years)
- Body Mass Index (BMI) (in kg/m^2)

The following categorical variables will be summarized using the categories reported in the eCRF:

- PS on ECOG scale (0 / 1 / 2 / 3 / 4)

In addition, hematology and biochemistry at baseline will be also analyzed.

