### 8.10.2 Laboratory abnormalities

The summaries will include all laboratory assessments collected from baseline assessment until 30 days after treatment discontinuation. All laboratory assessments will be listed and those collected more than 30 days after study treatment discontinuation will be flagged in the listings.

All laboratory values will be converted into SI units and will have a severity grade calculated using appropriate common terminology criteria for AEs (NCI-CTCAE, version 5). A listing of laboratory values will be provided by laboratory parameter and patient. A separate listing will display notable laboratory abnormalities (i.e., newly occurring CTCAE Grade 3 or 4 laboratory toxicities). The frequency of these notable laboratory abnormalities will be displayed by parameter. The shift tables using CTCAE grades to compare baseline to the worst post-baseline value will be produced for all relevant safety measures as described in the statistical analysis plan. Note that for parameters with two directions abnormalities (hypo/hyper), two tables will be presented.

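### As printed, the SAP rule for laboratory results recorded as `> x` multiplies the limit by 11, 2, 1.1 or 1.01 for one to four significant digits, where a small nudge above it was evidently meant; the practical effect is probably small

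*SAP*

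**What the plan says.** SAP 7.6.2 (Derived variable) gives two paired substitution rules for laboratory results outside the reportable range.

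- Below the range: "x = x * \sum_{i=1}^{n+2} (9 * 10^{-i})$ if value recorded as" `< x`.
- Above the range: "x = x * (1 + 10^{-n+2})$ if value recorded as" `> x`.

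Both come "with n denoted the number of significant" digits. The substituted number is used "for the calculation of descriptive parameters and for the value derived in standard units". Two qualifications follow. One is permissive: "Other methods could be investigated for specific parameters". The other protects the listings: "In individual listings, they will be presented as" `< x` or `> x`.

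Two other sections bear on where the substitute is used. On baseline data, SAP 8.3.1 says: "In addition, hematology and biochemistry at baseline will be also analyzed". On grading, SAP 8.10.2 says: "All laboratory values will be converted into SI units and will have a severity grade calculated" under CTCAE version 5.

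**The concern.** The two rules should be mirror images, one placing the value just inside the lower bound and the other just beyond the upper bound. The same n+2 appears in both. In the lower rule it is the upper limit of the sum, so more digits give a finer nudge. In the upper rule it sits in the exponent without a bracket, so the minus sign applies to n alone. For limits of one or two digits the result is then a multiple of the limit.

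If this is programmed literally, a censored result enters the baseline statistics as a number the laboratory never reported. SAP section 4 records 6 treated patients, so one such value is a sixth of a mean. There is also a conditional route to grading. If the CTCAE grade is calculated from the substituted standard-unit value, an analyte graded on the high side could show a grade that the recorded result does not support. That would reach the grade 3-4 listing (Table 14.3.4.1) or the shift tables (14.3.4.2.1 and 14.3.4.2.2).

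**Working it through.** **Inputs.** Both formulas and the meaning of n come from SAP 7.6.2. The number treated, 6, comes from SAP section 4. The SAP gives no worked example of the rule, so there is no plan figure to reproduce.

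**Step 1: the lower rule.** The sum of 9*10^-i for i = 1 to n+2 equals 1 - 10^-(n+2). For n = 1 this is 0.9 + 0.09 + 0.009 = 0.999.

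**Step 2: the upper rule as printed.** The multiplier is 1 + 10^(-n+2). For n = 1 this is 1 + 10^1 = 11, and for n = 2 it is 1 + 10^0 = 2.

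**Step 3: the upper rule as a mirror image.** The multiplier is 1 + 10^-(n+2).

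| n | `< x` multiplier | `> x` as printed | `> x` mirrored |
|---|---|---|---|
| 1 | 0.999 | 11 | 1.001 |
| 2 | 0.9999 | 2 | 1.0001 |
| 3 | 0.99999 | 1.1 | 1.00001 |
| 4 | 0.999999 | 1.01 | 1.000001 |

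**Step 4: order check.** This check does not depend on how trailing zeros are counted.

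- As printed, `>99` (n = 2) gives 99 * 2 = 198, and `>101` (n = 3) gives 101 * 1.1 = 111.1. The larger bound receives the smaller value.
- Mirrored, they give 99 * 1.0001 = 99.0099 and 101 * 1.00001 = 101.00101. The order is kept.

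**Step 5: trailing zeros.** The SAP does not say whether they count as significant. For an assumed result of `>90`:

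- n = 2: 90 * 2 = 180 as printed, 90 * 1.0001 = 90.009 mirrored.
- n = 1: 90 * 11 = 990 as printed, 90 * 1.001 = 90.09 mirrored.

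**Step 6: effect on a mean of six (assumed data, n = 2).** These values are illustrative and do not come from the documents.

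- Five patients at 75 and one `>90`: (5*75 + 180)/6 = 92.5 as printed, (5*75 + 90.009)/6 = 77.5 mirrored.
- Four patients at 75 and two `>90`: (4*75 + 2*180)/6 = 110 as printed, (4*75 + 2*90.009)/6 = 80.0 mirrored. The SD is sqrt[(4*35^2 + 2*70^2)/5] = 54.2 as printed and about 7.75 mirrored.

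**Step 7: where the substitute can go.**

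- *Descriptive statistics.* The stated use is the baseline hematology and biochemistry analysis in SAP 8.3.1. Protocol 6.2.1 counts creatinine clearance as biochemistry. SAP 7.6.2 accepts CKD-EPI and MDRD values alongside Cockcroft, and plans recalculation only for Cockcroft.
- *Grading.* SAP Appendix 3 lists the graded parameters. Creatinine is among them; creatinine clearance is not. A renal result such as `>90` therefore cannot move a grade. The grading route concerns other analytes, and only if grading uses the substituted value.

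**The case against.** **The bracket may have been lost in reading the PDF.** The point turns on one pair of brackets inside a superscript. The `< x` rule shows what was intended, but it fits a correct source formula that lost its bracket just as well as it fits a faulty one. This stands as a reason to look at the source first. A reader might infer that the programmed analysis is already wrong; the documents do not show that.

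**The reach is short.** A reader might infer that results such as `>60` or `>90` will appear in the summaries as 120 or 180, or that the safety findings will be inflated. The documents support neither.

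- They contain no such result and give no frequency for `> x` values.
- Cockcroft clearance is recalculated, and no method of clearance is graded.
- The SAP 10.1 table list has no dedicated table of continuous laboratory statistics. Its laboratory outputs are a grade 3-4 listing and two shift tables, and the patient listings in 10.2 keep `> x`.
- The primary endpoint is adverse events, which do not use this rule directly.
- No graded analyte has been identified for which a `> x` result would cross a grade limit.

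All of this stands, and it limits the consequence.

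**There are safeguards.** The SAP allows other methods for specific parameters, plans a data review meeting (7.2) and has draft outputs checked for inconsistency (7.5, 8.1). A summary value of 180 beside a listed `>90` might be noticed. But the permission names no method and no trigger, and a review might or might not catch the discrepancy. Neither corrects the default formula.

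**Dependence on digit count.** The size of the nudge varies with the number of digits in the `< x` rule and in the mirrored rule too, so that alone is not an error. The fault is that the printed rule turns a nudge into a multiple for short limits.

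**Conclusion.** The formula as printed is wrong if followed. It gives 11x, 2x, 1.1x and 1.01x for one to four significant digits and can reverse the order of two bounds, which no reasonable substitution rule does. The paired `< x` rule makes the intention clear.

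The size of the error depends on the limit. It is large for one or two digits, 10% for three, and 1% or less from four digits on. Its effect on reported results is probably small: the only stated descriptive use is the baseline hematology and biochemistry analysis, and the other laboratory outputs are mainly listings and grade shifts. Inflation of a high-side grade is possible for a graded analyte, but only if grading uses the substituted standard-unit value, which the SAP does not say outright. Renal examples such as `>90` affect descriptive statistics only.

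This rests on two assumptions: that the bracket is absent in the source as well as in the machine-read text, and that at least one `> x` result occurs. Neither can be settled from the documents. The point deserves correction because the rule is a default that can be programmed literally, not because damage to the trial's conclusions has been shown.

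**What to change.** 1. Check the source PDF of SAP 7.6.2 and the derivation program. If both already have the exponent as -(n+2), nothing in the formula needs to change.
2. If the bracket is absent, change the `> x` rule to x*(1 + 10^-(n+2)), so that it mirrors the `< x` rule, and correct the matching line of code.
3. State whether trailing zeros count as significant digits. Under the corrected rule the difference is trivial (90.009 against 90.09 for `>90`), but the derivation becomes reproducible.
4. Keep `> x` in the individual listings as already planned.

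The cost is one bracket and one clarifying sentence in the SAP, and one line of code. Data collection and study conduct are unaffected.

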**Creatinine Clearance (CRCL):**

**Creatinine clearance equation could be expressed as 3 methods: Cockcroft / CKD EPI / MDRD**

With Cockcroft formula Creatinine Clearance will be recalculated:

$$\text{CRCL(Females)} \text{ (mL/min)} = 1.04 \times \text{weight (kg)} \times (140 - \text{Age}) / \text{creatinine}(\mu\text{mol/L})$$

$$\text{CRCL (Females)} \text{ (mL/min)} = [(140 - \text{age})(\text{weight (kg)}) \times (0.85)] / (72) \text{ (serum creatinine in mg/dL)}$$

For the remaining time points, creatinine and weight values of corresponding time points will be used. If weight is missing, the closest compared to the actual date weight will be used.

## **8 STATISTICAL METHODS**

### **8.1 General principles**

Statistical summaries will be produced using SAS® software version 9.4. The tables, listings and graphics will be prepared in landscape format.

Drafts TFLs will be produced and reviewed before the database lock to ensure that no data is missing and to check for potential inconsistency in the database.

Continuous variables will be described using the number of observations (N), arithmetic mean (Mean), standard deviation (sd), minimum (MIN), median (Median), the interquartile range (Q1-Q3) and maximum (MAX). Means will be further described with 95% confidence intervals (CIs) where appropriate. One additional decimal point for mean, median, Q1 and Q3, and 2 additional decimal points for sd will be used. Data with more than 3 decimal places (if any), may not follow this rule: so, 3 decimal places will be used.

Categorical variables will be summarized by frequency (N) and percentage (%). Proportions will be estimated with their exact (Clopper-Pearson) 95% CIs when appropriate.

### **8.2 Patient enrollment and disposition**

#### **8.2.1 Screening status**

The number of patients screened (i.e., who signed informed consent) will be displayed. All patients who failed to meet eligibility criteria after ICF signature will be considered as screening failure and reported in the study report. The number of these patients and the primary reason for non-inclusion will be also displayed. Percentages will be calculated over the number of patients screened.

A listing will be performed to present all screen failures with the reason(s) of non-inclusion for each part (screening period and treatment period). The number of screening failure patients and reasons for screening failure and reasons will be summarized.

#### **8.2.2 Patient's populations**

The disposition data will be presented by patient in data listings and the following items will be presented in a summary table:

- The number of patients included who received at least one dose of TG4050 (**SAF**)
- The number of patients excluded from the populations and reasons for exclusion
- The number of patients who discontinued TG4050 and reasons for discontinuation TG4050

### **8.3 Analysis of demographic and baseline characteristics**

Analyses will be based on the SAF / EPP populations.

#### **8.3.1 Demographic and baseline characteristics**

Baseline demographics and disease characteristics data will be listed and summarized on SAF population.  
SAP-template version of 4 Jan 2024

The following continuous variables will be included:

- Date of ICF signature (listing only)
- Age at initial informed consent signature (years)
- Body Mass Index (BMI) (in kg/m^2)

The following categorical variables will be summarized using the categories reported in the eCRF:

- PS on ECOG scale (0 / 1 / 2 / 3 / 4)

In addition, hematology and biochemistry at baseline will be also analyzed.

### 8.3.2 History of studied disease

The following variables will be listed and/or summarized:

- Time since initial diagnosis (months)
- Stage before surgery (IIIC / IVA / Other)
- Stage after surgery (on resected tumor)
- Histological type (Serous carcinoma / Other)
- Primary tumor location (Ovary(ies) / Fallopian tube(s) / Peritoneum / Lymph node / Other)
- Presence of BRCA1/BRCA2 (Yes / No / Not Known)
- Other molecular tests (if applicable)
  - Result of test (Yes/No)
- Tumor totally resected (Yes / No)
  - If No: size of residual disease: microscopic / <=1cm / >1cm
- Date of post-adjuvant chemotherapy imaging
- Response on last imaging post-adjuvant chemotherapy (CR (non-evidence of disease) / PR / SD / PD / NE / Suspicious indeterminate nodule)
- 

### 8.3.3 Vital signs and electrocardiograms at baseline

The following variables will be listed and/or summarized:

- Weight (in Kg), Height (in cm)
- Body temperature (°C)
- Pulse rate (bpm)

- Systolic and Diastolic Blood Pressure (mmHg)
- Electrocardiogram (Normal / Abnormal Not Clinically Significant (NCS) / Abnormal Clinically Significant (CS))

### **8.3.4 Serology**

HCV Serology and detection of HBsAg and Blood sampling (for HLA typing) will be listed and/or summarized:

- HCV serology (Positive / Negative / Not Available)
- Hepatitis B surface Antigen (HBsAg) (Positive / Negative / Not Available)

### **8.3.5 Manufacturing**

Request to TG4050 Manufacturing will be listed:

- Type of sample (Frozen / Formalin-fixed)
- Tumor sample identification and date of shipment
- Date of blood sampling
- Blood sample identification
- Date of shipment

### **8.3.6 Prior anti-cancer therapies**

SAF population will be used for all summaries and listings of prior anti-cancer therapies. The SAF set will be used for all summaries and listings of prior anti-cancer therapies.

Prior anti-cancer therapies medications will be listed and summarized with the following items:

- Number of patients with previous therapy medication
- Medication (only listings)
- Type of therapy (Chemotherapy / Monoclonal antibody / PARP inhibitor / Other)
- Administration setting (Adjuvant / Neoadjuvant / Maintenance / Other)
- Time between last dose and first dose (days) for each type of prior anti-cancer therapy (months)
- Number of cycles of chemotherapy
- Time between last administration of chemotherapy and ICF signature (months)
- Duration of treatment (months)

### **8.3.7 Imaging until asymptomatic relapse**

During the screening period imaging will be performed in case of CA-125 increase or if symptoms or clinical signs occur. Data related to the imaging will be listed.

### **8.3.8 CA-125 serum concentration in blood**

CA-125 serum concentration in blood will be analyzed centrally (normal ranges 0 to 35 U/mL). Data related will be listed. If data are collected and recorded in eCRF, all data will be pooled and in case of data available at the same date locally and centrally, priority will be given to central data.

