### 8.2. Evaluation during the treatment period

#### 8.2.1. Efficacy evaluation

##### CA-125 evaluation

CA-125 concentration assessed in an accredited central laboratory will be measured every 3 weeks from the start of study treatment until treatment discontinuation for any reason including documented disease progression by RECIST 1.1. For patients who stopped the study treatment before documentation of disease progression, CA-125 measurements should then be performed every 9 weeks until documented progression. A CA-125 response is defined as at least a 50 %

reduction in CA-125 concentrations from a pretreatment sample according to GCIG criteria. The response must be confirmed and maintained for at least 28 days.

CA-125 doubling time and half-life as appropriate, time to normalization will also be analyzed during the study treatment period.

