#### 2.1.2 Treatment period

A treatment period with TG4050 monotherapy will start in:

- Cohort A: when patients develop an asymptomatic relapse defined on the basis of progressive serial elevations of serum CA-125 (GCIG criteria) or documentation of low volume radiological disease with CA-125 > ULN. Low volume radiological disease is defined as radiologically visible disease excluding intra-hepatic or intra-splenic metastases, ascites or pleural effusion thought to require drainage.
- Cohort B: when patients develop an asymptomatic relapse with measurable disease excluding intra-hepatic or intra-splenic metastases, ascites or pleural effusion thought to require drainage, whatever serum CA-125 level and for whom further treatment is not planned within 2 months. Longest

diameter on CT-scan must not exceed 2 cm for non-nodal lesions and 2.5 cm in short axis for nodal lesions.

Patients will receive TG4050 up to a total of 20 injections or until documented disease progression as defined by RECIST 1.1 justifying treatment with chemotherapy, or unacceptable toxicity including occurrence of a dose-limiting toxicity, or patient withdrawal for any reason, whichever occurs first.

All treated patients will be followed for:

- Safety assessments performed on a weekly basis for the first 6 weeks and every 3 weeks thereafter.
- Serum CA-125 levels assessed in an accredited central laboratory within 7 days prior to treatment initiation and every 3 weeks after start of study treatment.
- Imaging performed within 21 days prior to treatment initiation, at day 43 and every 9 weeks after study treatment start.
- Immune responses evaluated in the blood at baseline and on days 8, 22, 43, 64, 85 and 211; in the tumor at the time of documented disease progression according to RECIST 1.1.

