## 7.6 Definitions and Derived variables

### 7.6.1 Definitions

Screened patient: A patient having consented

Re-screened patient: A patient who did not meet eligibility criteria when initially consented. This patient may fulfill criteria later and will be re-consented for screening.

Screened failed patient: A screened patient never treated in the study for any reason.

Treated patient: A patient having received at least one TG4050 dose.

Completed patient: Patient will be considered as completer if she received the treatment until:

- Disease progression or until the maximum number of administrations has been reached (20 injections of TG4050)
- occurrence of an AE due to DLT or linked to progressive disease
- Death

Baseline: Unless otherwise specified, baseline is the last measurement taken prior to the first injection of TG4050.

Baseline assessment for efficacy evaluations: In the context of baseline definition, the efficacy evaluations include in particular tumor evaluations and CA125 measurement. If baseline assessment is missing, results obtained at Day 1 can be used if assessments were performed prior to first TG4050 injection.

Baseline assessment for safety evaluations: the last available assessment before first TG4050 injection. If patients have no assessment as defined above, the baseline result will be missing. Baseline can be D1 if assessment was done before first TG4050 injection.

Study day:

- From first treatment administration, study day will be calculated using the start date of treatment as the origin, i.e. the study day will be calculated as (date of assessment) – (start date of study treatment) +1. Then study day 1 will be the first day of first study treatment administration.
- For pre-study treatment administration measurements, the study day will be negative and calculated as (date of assessment) – (start date of study treatment).

Cut-off date: For a given analysis (safety, final and follow-up analysis), data in the database with a date prior or equal to the cut-off date must be as clean as possible for the analyses. The cut-off date will be the date of the export.

Time window (to check visits out of this window):

- For the visits:
  - +/- 1 day for the first 6 weeks
  - +/- 7 days beyond the first 6 weeks
- For the tumor assessment:

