## 10 LIST OF TABLES, FIGURES AND LISTINGS

### 10.1 Tables, figures and graphs

Table number	Title
14.1	DEMOGRAPHIC DATA
14.1.1	patients disposition
Table 14.1.1.1	Screen failure and non-inclusion reason – SCR
Table 14.1.1.2	Study populations
Table 14.1.1.3	Summary of protocol deviations – SCR
Table 14.1.1.4	Summary of protocol deviations – SAF
14.1.2	Demographic and Baseline characteristics
Table 14.1.2.1.1	Demographic data and study entry characteristics – SCR
Table 14.1.2.1.2	Demographic data and baseline characteristics – SAF
Table 14.1.2.2	Relevant Medical History and current Medical Conditions – SAF
Table 14.1.2.3	Signs and symptoms at baseline – SAF
Table 14.1.2.4.1:2	Prior anti-cancer therapies – SCR/SAF
Table 14.1.2.5	Vital signs and clinical examination – SAF
14.2	EFFICACY DATA
14.2.1	CA-125 Evolution
Figure 14.2.1 – 1	Waterfall plot for best percentage change of CA-125 – SAF
Figure 14.2.1 – 2	Evolution of CA-125 between Screening period and Treatment period – SAF
14.3	SAFETY DATA
14.3.1	Displays of adverse events
Table 14.3.1.1	Summary of adverse events – SAF
Table 14.3.1.2	Number (%) of patients with adverse events by cohort - SAF
Table 14.3.1.3	Number (%) of patients with adverse events by grade – SAF
Table 14.3.1.4	Number (%) of patients with adverse events related to TG4050 by grade – SAF
Table 14.3.1.5	Number (%) of patients with injection site reactions by grade – SAF
Figure 14.3.1.6	Adverse events by patient – SAF
14.3.2	Listings of deaths, other serious and significant adverse events
Table 14.3.2.1	Adverse events leading to treatment discontinuation, listing – SAF
Table 14.3.2.2	Adverse events due to DLT, listing – SAF
Table 14.3.2.3	Serious adverse events, listing – SAF
Table 14.3.2.4	Serious adverse events related to TG4050, listing – SAF
Table 14.3.2.5	Grade 3/4 adverse events, listing – SAF
Table 14.3.2.6	Fatal Adverse Events, listing – SAF
Table 14.3.2.7	Deaths, listing – SAF
14.3.3	Narrative of deaths, other serious and certain other significant adverse events
14.3.4	Abnormal Laboratory Value (each patient)
Table 14.3.4.1	Laboratory parameters Grade 3-4, listing – SAF

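### SAP 8.3.8 pools local and central CA-125 without tying baseline and follow-up to one laboratory, so the two CA-125 figures can mix laboratories within a patient

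*SAP*

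**What the plan says.** **Scheduled source.** The protocol's CA-125 evaluation (section 8.2.1) states: "CA-125 concentration assessed in an accredited central laboratory will be measured every 3 weeks from the start of study treatment". SAP 2.1.2 agrees and adds the pre-dose sample: "Serum CA-125 levels assessed in an accredited central laboratory within 7 days prior to treatment initiation and every 3 weeks after start of study treatment". For patients who stop treatment before progression, Protocol 6.2.5 and 8.2.1 ask for CA-125 every 9 weeks, and those sentences do not name the laboratory.

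**Analysis source.** SAP 8.3.8 opens with central analysis: "CA-125 serum concentration in blood will be analyzed centrally (normal ranges 0 to 35 U/mL". It then provides for values recorded in the eCRF as follows: "all data will be pooled and in case of data available at the same date locally and centrally, priority will be given to central data".

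**Baseline.** SAP 7.6.1 says that, unless otherwise specified, "baseline is the last measurement taken prior to the first injection of TG4050". A separate entry for efficacy baselines says that "the efficacy evaluations include in particular tumor evaluations and CA125 measurement", and adds: "If baseline assessment is missing, results obtained at Day 1 can be used if assessments were performed prior to first TG4050 injection". Neither entry mentions a laboratory.

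**Outputs.** SAP 10.1 lists two CA-125 figures, both on the SAF: Figure 14.2.1-1, "Waterfall plot for best percentage change of CA-125", and Figure 14.2.1-2, which follows CA-125 from screening into treatment. Listings 16.2.4.5 and 16.2.6.1 give the individual values. GCIG response is still named among the secondary endpoints in SAP 3.2, but SAP 8.8 gives no analysis for it and no output is listed.

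**The concern.** A within-patient percentage change is interpretable when numerator and denominator come from the same assay. If two laboratories read the same serum differently by a constant factor, that factor cancels within one laboratory. It does not cancel when baseline comes from one and follow-up from the other.

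The central-priority rule protects against this only when a local and a central value carry the same date. A local value on its own date stays in the pooled series and competes on equal terms: for baseline if it is the latest before the first injection, or for best change if it is low and recorded on treatment. The documents contain no requirement that baseline and follow-up share a laboratory, no assay adjustment and no instruction to flag the source.

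At stake is the reading of the only two CA-125 summaries left in the output list. With six treated patients, each bar of the waterfall will be looked at individually.

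**Working it through.** The plan has no assay-agreement figure, power calculation or CA-125 test to reproduce. The check is therefore which combinations the rules allow, and what each does to a percentage change.

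**Step 1: what the rules allow.** Setting the source rule (SAP 8.3.8) beside the baseline rule (SAP 7.6.1) and the central sampling schedule (Protocol 8.2.1, SAP 2.1.2):

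- Central pre-dose sample, then a later local value still before injection: local baseline, central follow-up.
- Central pre-dose sample missing, local value present: local baseline, central follow-up.
- Central baseline, and a local value on its own date during treatment: the local value becomes a candidate for best change.
- After treatment is stopped: laboratory unnamed, so either source is possible. Whether these values enter the best change is not stated.

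**Step 2: local baseline, central follow-up.** Let *r* be the local reading divided by the central reading of the same serum, *d* the true change and *B* the baseline on the central scale. The documents give no value for *r*, so it is assumed constant and shown over a range.

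Apparent change = B(1 + d)/(rB) - 1 = (1 + d)/r - 1.

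Setting this to -0.5, the true fall that reads as 50% is 1 - 0.5r.

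| r | Apparent change if d = 0 | True fall that reads as 50% |
|---|---|---|
| 0.8 | 1/0.8 - 1 = +25.0% | 60.0% |
| 0.9 | +11.1% | 55.0% |
| 1.0 | 0.0% | 50.0% |
| 1.1 | -9.1% | 45.0% |
| 1.25 | 1/1.25 - 1 = -20.0% | 37.5% |
| 1.5 | -33.3% | 25.0% |
| 2.0 | 1/2 - 1 = -50.0% | 0.0% |

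The distortion runs both ways. At r = 0.8 a true 50% fall reads as 0.5/0.8 - 1 = -37.5%. At r = 1.2 a true 20% rise reads as 1.2/1.2 - 1 = 0%.

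**Step 3: central baseline, one local value on treatment.** Apparent change = r(1 + d) - 1. With d = 0 this is -20% at r = 0.8 and -10% at r = 0.9. If best change means the lowest value (the SAP does not define it), a low local value is kept, while a high one is passed over when central values are also available. This route therefore works in one direction only.

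**Step 4: one laboratory throughout.** Apparent change = rB(1 + d)/(rB) - 1 = d. The artefact is zero for any constant r.

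**Step 5: weight.** SAP section 4 reports 6 treated patients, so one affected patient is 1/6 = 16.7% of the bars.

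**The case against.** The case on the other side has several parts.

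- **The trigger is hypothetical.** No section schedules a local CA-125 near dosing or on treatment, and the planned samples at those times are central. This stands: the risk is conditional and its frequency unknown. The SAP does, however, write a rule for local values, so it allows for their existence.
- **The efficacy baseline entry may already point to the central sample.** It admits Day 1 results only when the baseline assessment is missing, which can be read as making the scheduled central assessment the primary source. That reading is possible, but the entry names no laboratory and does not say what happens when a later local value exists.
- **SAP 8.3.8 sits among the baseline characteristics and says the data will be listed.** Its reach to the figures is inferred, since SAP 8.8 has no CA-125 rule. This stands as a limit. It does not remove the problem: if pooling governs baseline only, a pooled baseline against central follow-up is the mismatch described above.
- **The consequences are small.** CA-125 is secondary and descriptive, with no test or comparator. This stands.

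A reader might go further and infer that local values are read against the wrong limit, because the 0 to 35 U/mL range is given with the central analysis. Little follows from that: SAP 3.2 drops time to normalization, and neither figure is defined by the upper limit. A reader might also infer false GCIG responses. The documents do not support that as a general risk. No response output is listed, and Protocol 8.2.1 requires the fall to be confirmed and held for at least 28 days, so one low local value is not enough. A mismatched baseline could persist through confirmation, but within the assumed range it could only move a patient whose true fall was already substantial.

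**Conclusion.** The point holds as a gap in the rules. As written, SAP 8.3.8 and 7.6.1 permit a percentage change, and a plotted series, built from two laboratories in the same patient. Under an assumed local/central ratio of 0.8 to 1.25, a local baseline with central follow-up and no true change would read between +25% and -20%. A 50% fall from laboratory difference alone needs a ratio of about 2. These sizes rest entirely on the assumed, constant ratio.

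It would be tempting to conclude that the pooling rule undoes the central-laboratory design, or that the figures will show laboratory differences as a drug effect. The documents do not support either. Central remains the scheduled source at baseline and on treatment and takes priority on shared dates, the number of local values is not given, and the bias from a local baseline has no fixed direction. Two descriptive figures in six patients carry no formal efficacy claim, and the primary safety endpoint does not use CA-125. This is a cheap improvement to secondary descriptive outputs.

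**What to change.** Amend SAP 8.3.8 as follows:

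- CA-125 baseline, percentage change, Figures 14.2.1-1 and 14.2.1-2, and GCIG response if it is derived, use a single laboratory source per patient, central by default.
- CA-125 baseline is the last central value before the first injection. Cross-refer to this from SAP 7.6.1.
- If a patient has no central baseline, use one laboratory throughout for her and mark her in the figure.
- Other local values stay in Listings 16.2.4.5 and 16.2.6.1, flagged as local.

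The same source rule should cover the 9-weekly values after treatment is stopped, for which the laboratory is not named.

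The work is a short text change and a filter on laboratory source. The downside is that points with only a local value drop out of the figures; among six patients this could leave a few points, or possibly one bar, missing or marked. The flagged listings keep every value visible.
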